4.5 Discontinuation Criteria

Patients may withdraw voluntarily from participation in the study at any time and for any

reason. They may want to withdraw because of increased constipation off laxatives, nausea,

vomiting or diarrhea.

Patients may be withdrawn on the basis of the medical monitor safety and tolerability

review or the Investigator's clinical judgment, protocol deviation, change in dose of medications

unrelated to study medication or loss to follow-up.

This study may be terminated at the discretion of the Enterin, Inc. or of any regulatory

agency for reasons including safety and/or efficacy.

An Investigator may elect to discontinue or stop the study at his or her site for any reason

including safety.

When a patient withdraws or is withdrawn before completing the study, the date and reason

for withdrawal are to be documented in the eCRF. The study site must immediately notify the

medical monitor. Patients who withdraw prematurely are to attend an early discontinuation visit

if possible, at which time they will complete all assessments.

In the event that a patient is withdrawn prematurely due to an AE or serious AE, the AE or

serious AE will be followed until it resolves or stabilizes, or until it is judged by the Investigator

to be no longer clinically significant.

CP1001 v0.9, Version Date: 27JUL2017

41

4.6 Concomitant Medication

- Preventive laxatives will be discontinued during the run-in period. Throughout the study,
 patients will be allowed to take constipation *rescue medication on demand*, and only if
 they have not had a bowel movement in three consecutive days.
- In stage 1, rescue medication (laxative, bulking agent, softener, suppository) can be taken as needed and as stated above, and noted in the stool chart. Rescue medication cannot be taken during the 24 hrs before or after study medication. Any bowel movement produced within 24 hours of rescue medication will not be counted.

In Stage 2, rescue medication (Dulcolax suppository and/or enema) can be taken on demand during the run-in period as stated above and noted in the stool diary. During the dosing period, rescue medication is taken on the evening of the third dose at any given level if a stool has not been produced in response to three days of study medication. Enterin CMO should be consulted for any questions related to rescue medication. Rescue medications will be recorded in the daily diary. Bowel movement produced within 24 hours of rescue medication will not be counted as either spontaneous bowel movement or complete spontaneous bowel movement.

- In both stages, protein pump inhibitors will be discontinued during the run-in period and reinstated during the wash-out period.
- Benzodiazepines, hypnotics, other sedatives, barbiturates, and opiates will not be allowed.
 All medications shall be reviewed and dis/approved by the investigator on a case-by-case basis.
- Selective serotonin reuptake inhibitor (SSRI), SNRI, tricyclic antidepressants anticholinergics, anti-histamines and anti-psychotics are permissible at stable doses.
- Dopamine agonists and amantadine will be allowed if on a stable dose for at least 4 weeks preceding the study.
- Deep brain stimulation is allowed at the PI's discretion.

5 STRATIFICATION AND RANDOMIZATION (STAGE 2)

Participants will be randomly assigned to study drug or placebo in block sizes of 4 according to a schedule provided by the study statistician. Patients will be stratified according to constipation severity. We will compare results in patients with average complete spontaneous stool frequency of 0-1 per week with those of patients with an average frequency of 1-2 per week. Patients will be blinded throughout the study until all data are analyzed and locked.

6 UNBLINDING

Patients will be unblinded under the following circumstances:

- Patient is terminated from the study
- Patient drops-out of the study
- A SAE occurs

7 MATERIALS

7.1 Study Drug

All study medications will be supplied by Enterin Inc. Ent-01 will be supplied as 25mg tablets packaged in white opaque high density polyethylene (HDPE) bottles with child-resistant closures. The placebo tablets will be identical in configuration and packaged similarly.

7.2 Packaging and Labeling

The study medication will come packaged in a white bottle containing 10 tablets. Tablets can be divided between patients as appropriate. To ensure blinding the packages will be identified as A, B, or C, and each will contain 10 tablets, all equal in appearance.

7.3 Storage, Dispensing and Reconciliation of Study Drug

All study medication must be stored in a locked, limited access area. Both the used and unused study medication should be stored at $2 - 8^{\circ}\text{C}$ (35.6 - 46.4°F).

Identity of Investigational Products				
Product Name	ENT-01	Placebo		

Dosage form	Tablets (mg)	Tablet
Dosage levels(mg)	25	Identical, but absent active
Route/dosage Oral. Doses above 25 mg will require multiple tablets:		Oral
	25 mg=1 tablet	
	50 mg=2 tablets	
	75 mg=3 tablets	
	100 mg=4 tablets	
	125 mg=5 tablets	
	150mg=6 tablets	
	175mg=7 tablets	
Dosing Instructions	Take 60 min before breakfast with 8 oz. water	Take 60 min before breakfast with 8 oz. water

8 WARNINGS AND PRECAUTIONS

Patients will be advised to stay at home for 4-6 hours after taking the first dose of medication in case they need to evacuate urgently. Beyond the first dose, patients themselves will be in a position to know if and when to leave the house.

9 STUDY PROCEDURES

9.1 Sitzmarks assessment of colonic motility in Stage 2

On Day 8 of the run-in period and again on Day 3 of the randomized period, patients will be reminded to self-administer a Sitzmarks capsule (contains 24 radiopaque markers; Konsyl Pharmaceuticals, Texas, USA). The patient will be instructed to abstain from using suppositories or enemas if possible until they return on Day 11 (or day 6 of randomized period). If they have to use suppositories on day 11 (or Day 6 of randomized period), make sure it's recorded in the daily diaries. An abdominal XR will be scheduled for Day 11 of run-in and Day 6 of randomized period.

On Day 11 of the run-in Period and again on Day 6 of the randomized period, an abdominal XR will be performed to determine the location and the extent of elimination of the radioisotope markers. Patients who expel at least 80% (19 or more of the markers) have grossly normal colonic transit. If remaining markers are scattered about the colon, the condition is most likely hypomotility or colonic inertia. If remaining markers are accumulated in the rectum or

rectosigmoid, the condition is most likely functional outlet delay. For patients whose markers accumulate in the rectosigmoid or when markers are retained diffusely, instruct patient to maximize liquid intake for the next two weeks.

9.2 Observations and Measurements

All the questionnaires will be filled in according to the schedule. In Trail-Making B, the Trail will be completed twice, and both results will be reported. If the patient fails to complete the Trail, it will be reported as failed to complete.

Stool diaries and sleep diaries: Patients will be instructed how to fill the diaries daily throughout the study. They will be told to mark use of suppositories or enemas.

Vital signs: Per study procedures listings and for PK subjects Randomization Day 1 and Day 6 before dose and 2 hours after dose.

An I-Button which measures skin temperature and attached to a wrist band will be worn for 5 consecutive 24 hr periods from day 8-13 during Period 1, throughout the dosing period and randomized period and for the first five days of the wash-out period, and will not be removed except for brief periods during a bath/shower. Patients will be shown how to wear the I-Buttons with the button facing the skin and overlying the radial artery.

9.3 Informed Consent

The Principal Investigator(s) at each center will ensure that the patient is given full and adequate oral and written information about the nature, purpose, possible risk and benefit of the study. Patients must also be notified that they are free to discontinue from the study at any time. The patient should be given the opportunity to ask questions and allowed time to consider the information provided.

9.4 Instructions to Patients

Prior to entry into the study, patients and their spouse/companion will be taught how to fill in the daily diaries for stool and sleep. They will be instructed about the use of rescue medication and told to record it in the diary. They will also be shown how to wear the I-Button and how to use the actigraphy device (See Appendix).

9.5 Clinical Laboratory Procedures

The following tests will be obtained at baseline and at the end of each Period.

- CBC
- Chemistry
- PT/PTT
- Pregnancy test
- Urinalysis

PK Samples for 10 selected subjects:

Timed blood samples (5.0 mL) will be collected into potassium-EDTA treated tubes for analysis of ENT-01 and its metabolite plasma concentrations.

Blood samples for PK analysis will be collected at the following times before and after dosing on the day before randomization and on Day 6 of the randomized period: 0 (pre-dose), 60 min, 2, 4, 8 hrs.

Once collected, PK samples will be stored in a -20°C or -70°C freezer until time of shipment. Labels and appropriate shipping materials will be provided to sites.

The concentration of study drug will be determined from the plasma samples using a validated analytical method. Details of the method validation and sample analysis will be included with the final clinical study report.

9.6 Other Procedures

Patients will fill in the following daily diary for stools (example inserted):

	Scale 1-7 1.Hard lumps	1.Manual disimpaction	Yes/No	or laxative Yes/No/list med
	2.Lumpy sausage	2.Enema needed		
	3.Cracked sausage	3.Straining needed		
		2.Lumpy sausage 3.Cracked	2.Lumpy sausage 2.Enema needed 3.Cracked 3.Straining	2.Lumpy sausage 2.Enema needed 3.Cracked 3.Straining needed

			4.Smooth sausage	5.Urgent without pain		
			5.Soft lumps	6.Urgent with pain		
			6.Mushy	7.Incontinent		
			7.Watery			
3/20	-	Yes	1	2	No	Yes/suppos
3/21	100	Yes	3	4	No	No
3/22	100	Yes	3	4	Yes	No
3/23	100	Yes	4	4	Yes	No
3/24	100	Yes	4	4	Yes	No
3/25	100	Yes	3	4	Yes	No

9.7 CTCAE Definitions of Dose Limiting Adverse Events

Adverse event	Grade 1	Grade 2	Grade 3	Grade 4	Grade 5
Diarrhea (watery stool)	Increase of <4 stools a day over baseline	Increase of 4-6 stools a day over baseline	Increase of >7 stools a day; incontinence; hospitalization indicated	Life threatening complications; urgent intervention indicated	Death
Vomiting	1-2 episodes per 24 hrs	3-5 episodes per 24 hrs	6 or more episodes in 24 hrs; tube feeding, TPN or hospitalization indicated	Life- threatening consequences; urgent intervention indicated	Death
Abdominal pain	Mild pain	Moderate pain; limiting instrumental ¹ ADL	Severe pain; limiting self- care ADL ²	-	-
Postural hypotension ³	Mild, transient lightheadedness or dizziness	Moderate lightheadedness, dizziness or	Severe lightheadedness, dizziness or	Life- threatening and urgent	Death

upon rising	fainting upon	fainting upon	intervention
from lying or	rising from	rising from	indicated
sitting position	lying or sitting	lying or sitting	
that does not	position that	position that	
interfere with	limits	limits self-care	
ADL	instrumental	ADL; Medical	
	ADL; Non-	intervention or	
	urgent medical	hospitalization	
	intervention	indicated	
	indicated		

Preparing meals, shopping for groceries or clothes, using the telephone, managing money, etc.

9.8 Criteria for DLT Endpoints:

Recurrent vomiting: 3-5 episodes of vomiting within 24 hours of taking ENT-01 (Grade 2 AE)

Recurrent diarrhea: 4-6 episodes of diarrhea within 24 hours of taking ENT-01 (Grade 2 AE)

Abdominal pain: Moderate pain that limits instrumental activities of daily living within 24 hours of taking ENT-01 (Grade 2 AE)

Postural hypotension: Moderate dizziness, lightheadedness or fainting upon rising from lying to sitting or standing and severe enough to require medical intervention within 24 hours of taking ENT-01 (Grade 2 AE) or either a systolic blood pressure less than 80mmHg or diastolic blood pressure less than 40mm Hg.

9.9 **Pre-Existing Medical Conditions**

All subjects enrolled in the study will have Parkinson's disease. Specific pre-existing medical conditions that will be excluded are listed in patient exclusion criteria.

9.10 Treatment Emergent Adverse events

Treatment-emergent adverse event (TEAE) is defined as any event not present prior to the initiation of the treatments or any event already present that worsens in either intensity or frequency following exposure to the treatments.

AE is typically collected after signing the informed consent form and could be related or unrelated to the study drug. TEAE is for after the subject actually taking the study drug.

²Bathing, dressing and undressing, feeding self, using the toilet, taking medications, and not bedridden

³Definition adapted from combining CTCAE definitions for Hypotension and Dizziness

AEs may be called "baseline-emergent adverse event" which is defined as any event which occurs or worsens during the staged screening process (after informed consent) including the randomization visit. We will include separate summaries for AEs that occur prior to the initiation of the treatment and AEs that occur after the initiation of the treatment (i.e., summary of treatment emergent adverse events).

9.11 Laboratory Abnormalities

Clinical labs will be performed by a local laboratory. Labs to be drawn during the study include: serum chemistries, a hematology panel and urinalysis. A serum pregnancy test must be performed and the result must be negative prior to the entry of women of child bearing potential. The investigator must obtain verification that the local laboratory meets the standards for quality and consistency set by the College of American Pathologists.

Clinical laboratory reports must be reviewed by a physician for out-of-range values within 24 hours of receipt. Out-of-range values will be evaluated using the following notations:

- NS Not clinically significant
- LE Laboratory Error
- PT Patient abnormal; relates to the patient's usual state of health
- SG Significant, other. This value cannot be explained by any of the other flags.

By definition a lab value flagged as "SG" must be entered on the adverse clinical laboratory event page in the case report form. A laboratory test flagged "SG" must be repeated as soon as possible. The investigator may use his/her own judgment as to whether the abnormal finding is sufficient reason to immediately withdraw the patient from the study.

If a laboratory value is considered to be serious and life-threatening the patient should be immediately discontinued from the study and appropriate therapy started. Refer to sections **9.7-9.12** for definition of a serious adverse event and related terms, and to sections **9.13-9.16** for details on reporting a serious adverse event.

9.12 AE Assessment and Recording

All adverse events, exacerbations of concomitant illnesses, or events known to be related to underlying disease processes or concomitant medications are to be recorded on the case report form throughout the study. If a pre-existing condition worsens on study, the date on which the

exacerbation began should be recorded. Onset dates for study treatment-related adverse events

must be on or after the date of initial study treatment use. The need to record an adverse event on

the case report form is not dependent on whether the adverse event is associated with the use of

the study medication. In order to avoid vague, ambiguous or colloquial expressions, the adverse

event should be recorded in standard medical terminology.

Adverse event recording will include the date of onset, severity, duration, whether or not

the study medication was discontinued or its dosage changed because of the event, the treatment

given and the outcome. The investigator must also assess whether the event was related to the

study medication, concurrent drug therapy, underlying disease, a combination of these factors, or

if it is unknown. Patients with an adverse event should be carefully followed to determine

outcome.

The investigator will use the NCI definitions to grade the severity of the event.

Grade 1: Mild; asymptomatic or mild symptoms; clinical or diagnostic observations

only; intervention not indicated

Grade 2: Moderate; minimal, local, or non-invasive intervention indicated; limiting age-

appropriate ADL

Grade 3: Severe or medically significant but not immediately life-threatening;

hospitalization or prolongation of hospitalization indicated; disabling; limiting

self-care ADL

Grade 4: Life-threatening consequences; urgent intervention indicated

Grade 5: Death

The relationship or association of the study medication in causing or contributing to the

adverse event will be characterized as remote, possible or probable as defined below:

Not related: Evidence indicates no plausible direct relationship to the study medication

CP1001 v0.9, Version Date: 27JUL2017

50

Remote: Suggests other conditions are reasonably likely to account for the event including concurrent illness, progression or expression of the disease state, or reaction to concurrent medication

Possible: Suggests that the association of the event with the study medication is unknown; however, the adverse event is not reasonably supported by other conditions

Probable: Suggests that a reasonable temporal sequence of the event with medication administration exists and, based upon the investigator's clinical experience, the association of the event with study medication seems likely

Definite: Suggests that based upon the investigator's experience, the association of the event with the study medication seems very certain.

Procedures such as surgery should not be recorded as adverse events. However, the medical condition for which the procedure was performed should be reported if it meets the definition of adverse event.

9.13 Reporting Requirements

Any adverse event, including both observed or volunteered problems, complaints, or symptoms that begins any time between the start of the first dose and within 30 days after the end of the last dose are to be recorded briefly on the appropriate case report form and in detail in the source documents. A check list of adverse events may not be used during this study.

The following are specific definitions that are relevant to meeting your reporting obligations and which are included in the FDA Regulations, 21CFR Part 312.32, and International Conference on Harmonization of Technical Requirements for Registration of Pharmaceuticals for Human Use (ICH) Guidelines:

Adverse Event: Any untoward medical occurrence in a patient administered a pharmaceutical product and which does not necessarily have to have a causal relationship with this treatment. An adverse event can be any unfavorable sign (including an abnormal laboratory finding), symptom, or disease temporally associated with the use of the investigational drug, whether or not considered related to the investigational drug.

Serious Adverse Event: An untoward event or reaction that at any dose:

- results in death
- is life-threatening
- requires inpatient hospitalization
- prolongs existing hospitalization
- results in permanent or significant disability or incapacity
- is a congenital anomaly/birth defect
- requires intervention to prevent permanent impairment/damage

Life-threatening: An event which a patient was at risk of death at the time of event.

There is a distinction between the severity and the seriousness of an adverse event. Severe is a measurement of intensity, thus a severe reaction is not necessarily a serious adverse event. For example, a headache may be severe in intensity, but would not be serious unless it met one of the criteria for serious adverse events listed previously.

9.14 Serious Adverse Events

Adverse events (AEs) and serious adverse events (SAEs) will be collected from the start of study treatment until the follow-up contact. Medical occurrences that began prior to the start of study treatment, but after obtaining informed consent were recorded on the Medical History/Current Medical Conditions CRF. The investigator or site staff will be responsible for the detection and documentation of events meeting the criteria and definition of an AE or SAE, as provided in the study protocol,

However, any SAEs assessed as related to study participation (e.g., dosing, protocol mandated procedures, invasive tests, or change in existing therapy) or related to a concomitant medication will be recorded from the time a subject consents to participate in the study up to and including any follow-up contact.

In the event of an AE or SAE, it will be the responsibility of the Investigator to review all documentation (e.g., hospital progress notes, laboratory, and diagnostics reports) relative to the event and attempt to establish a diagnosis of the event based on signs, symptoms, and other clinical information. The diagnosis was to be documented as the AE/SAE and not the individual's signs/symptoms. Once an Investigator becomes aware that an SAE has occurred in a study subject, they are to report the information to Enterin within 24hrs and provide an assessment of causality.

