Participants will receive a phone call and be asked about adverse events. They will also provide their daily stool chart to assess the severity of the constipation and use of laxatives, softeners, bulking agents and suppositories. *Patients with two or fewer complete, spontaneous bowel movements will qualify for the treatment period. A bowel movement occurring within 24 hours of suppository, softener, bulking agent or enema use will NOT be counted. A spontaneous stool is a stool occurring in the absence of a laxative, softener, bulking agent or suppository.* PAC-SYM and PAC-QOL to be administrated on day 14, or at the clinic at Dose 1 visit the following day if they fail to bring the completed survey.

PERIOD 2.1 (Stage 1): Single dose

Safety, tolerability and pharmacokinetics of orally administered single-dose ENT-01 in Sentinel Group

Duration: 22-57 days

The 10 patients in the sentinel group will be assigned to Cohort 1 and will participate in 8 single dosing periods.

Subjects	D1	D4-8	D7-15	D10-22	D13-29	D16-36	D19-43	D22-50	D25-57
1-2	25mg	50mg	75mg	100mg	125mg	150mg	175mg	200mg	
3-4		25mg	50mg	75mg	100mg	125mg	150mg	175mg	200mg
5-6		25mg	50mg	75mg	100mg	125mg	150mg	175mg	200mg
7-8		25mg	50mg	75mg	100mg	125mg	150mg	175mg	200mg
9-10		25mg	50mg	75mg	100mg	125mg	150mg	175mg	200mg

All 10 patients will be pre-selected in advance of check-in for their first scheduled dosing period. All laxatives, suppositories, softeners, bulking agents and enemas will be disallowed during the 24-hour period before or after the administration of study medication. Patients will wear the I-Button continuously for the entire dosing period. The first two patients (subjects 1-2) will first be admitted and given a single dose. The study will be conducted at a hospital-based clinical unit and patients will be monitored for 24 hours after the dose. Unless there are any safety

concerns, patients will be released at this time and brought back for the next dosing on Day 4-8 (D4-8), after a minimum of a 72 hour observation period. Dopamine will be taken prior to the clinic visit on an empty stomach. Patients will self-administer the study medication during their clinic visit. The dose will be taken on an empty stomach along with 8 oz. of water after baseline observations in the clinic. The patient will not be allowed to ingest any food for at least 60 minutes after study medication.

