Similarly, in tabulation by relationship,

- For a given preferred term, the most closely related preferred term to the study drug for each subject will be included.
- For a given system organ class, the most closely related system organ class to the study drug for each subject will be included.

Adverse events including baseline AEs, serious adverse events, and adverse events leading to discontinuation from the study will be provided in separate data listings.

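### Events between consent and first dose fall under contradictory collection rules, and the SAP reduces the promised pre-treatment AE summary to a listing without saying so

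*Protocol*

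**What the plan says.** Protocol 9.10 describes AE collection as running from consent and commits to reporting both phases: "We will include separate summaries for AEs that occur prior to the initiation of the treatment and AEs that occur after the initiation". Section 9.12 asks for all AEs on the CRF for the whole study. The Stage 1 call on run-in Day 14 asks directly: "Participants will receive a phone call and be asked about adverse events". The schedules in protocol Appendix 2 and SAP Tables 2 to 4 mark AE review during run-in.

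Two other protocol sections say otherwise. Section 9.13 limits recording to an event that "begins any time between the start of the first dose and within 30 days after the end of the last dose". Section 9.14 states that AEs and SAEs "will be collected from the start of study treatment until the follow-up contact", and that occurrences before study treatment "but after obtaining informed consent were recorded on the Medical History/Current Medical Conditions CRF". It makes one exception: SAEs judged related to study participation or to a concomitant medication "will be recorded from the time a subject consents to participate in the study up to and including any follow-up contact".

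SAP 7.8.1 tabulates AEs by dose level, fixed dose and washout, and separately for placebo and ENT-01 in the randomized period. Run-in events appear only here: "Adverse events including baseline AEs, serious adverse events, and adverse events leading to discontinuation from the study will be provided in separate data listings". SAP 5.1 reports no changes from the protocol's analyses. SAP section 9 reports two dropped analyses, both of the efficacy success endpoint.

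**The concern.** Safety and tolerability are primary objectives in both stages. In Stage 2, dose escalation and the fixed-dose period have no concurrent control, and the February 2018 amendment removed the randomized period.

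At the start of the Stage 2 run-in, patients stop laxatives, sedatives, hypnotics and opiates. Under the July 2017 protocol they also stop proton pump inhibitors; SAP Table 4 lets these continue to the end of run-in. Bowel, sleep and dizziness complaints may therefore appear before any ENT-01. SAP 7.8.1 names nausea, diarrhea and dizziness as events of special interest. How often such complaints arise before exposure helps in reading the on-treatment tables.

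TEAE status is also at stake. Protocol 9.10 and SAP 7.8.1 both count worsening as treatment-emergent, and judging that requires a severity before first dose. An AE record carries a grade. The documents do not show whether a medical-history entry does.

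**Working it through.** The plan states no figure on this point, so there is none to reproduce. The check sets the rules side by side and then sizes the periods.

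**Rules for an event between consent and first dose**

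| Source | Rule |
|---|---|
| Protocol 9.10 | Collected as an AE after consent; separate pre-treatment summary promised |
| Protocol 9.12 | Recorded as an AE on the CRF throughout |
| Protocol Appendix 2; SAP Tables 2–4 | AE review scheduled in run-in; SAP Table 4 marks it from Day 1 |
| Protocol 9.13 | Outside the AE window, which opens at first dose |
| Protocol 9.14 | Medical History CRF, except SAEs related to participation or a concomitant medication |
| SAP 7.8.1 | Listed, not tabulated |
| SAP 5.1 and section 9 | Change not mentioned |

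A site cannot follow 9.10 and 9.12 and also follow 9.13 and 9.14 for a non-serious run-in event. If sites choose differently, the AE data set holds run-in events for some patients and not for others. SAP 2.1 describes the amendment as changing only the dose range and the randomized period, so on the SAP's account these rules carry over.

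**Planned Stage 2 time off drug, if all 40 patients complete each period**

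- Run-in: 40 × 14 = 560 patient-days, all before ENT-01 (Stage 2 patients did not take part in Stage 1).
- Washout: 40 × 14 = 560 patient-days, all after ENT-01. Original medications including laxatives restart in week 2, so 40 × 7 = 280 precede the restart.
- Placebo in Period 4, July 2017 design: 20 × 6 = 120 patient-days, after 5 to 7 days on the pro-kinetic dose.
- Placebo after the amendment: the number treated is not given. Assuming 2 to 10 patients, 2 × 6 = 12 to 10 × 6 = 60 patient-days. That is 12/560, about 1/47, to 60/560, about 1/9, of run-in time.

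**Illustration only.** The documents give no background AE rate. Assume that a proportion b of patients has an event in 14 days off drug and that the rate is constant. The proportion with an event in d days with no drug effect is then 1 − (1 − b)^(d/14).

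| Assumed b | 5 days | 7 days | 17 days | 25 days |
|---|---|---|---|---|
| 10% | 4% | 5% | 12% | 17% |
| 20% | 8% | 11% | 24% | 33% |
| 30% | 12% | 16% | 35% | 47% |

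Five to 7 days is the time in Period 3.2 for a patient who responds at the first dose level. Seventeen days is the Period 3.2 limit in the design table, and 25 is the Stage 2 maximum in protocol section 11. The spread, 4% to 47%, shows that background incidence cannot be guessed. It does not estimate it.

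**The case against.** Much of the information may survive. Section 9.12 and the schedules call for AE capture in run-in, and a listing of baseline AEs implies that the SAP expects them in the AE data. In Stage 2, medical history is MedDRA-coded and tabulated (SAP 7.4.3). The 9.14 exception covers serious events from a change in existing therapy. Section 9.12 asks for the date when a pre-existing condition worsens. Protocol 10.3.1, which sets out the AE summaries, does not repeat the 9.10 promise. All of this stands, and it limits the point to data at risk. It does not remove the conflict. Medical-history tables mix run-in events with older conditions, the exception leaves out non-serious events, and an exacerbation date is not a pre-dose grade.

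A reader might infer that run-in is the trial's only no-drug reference, or that the trial is uncontrolled. The documents support neither. SAP 7.8.1 also tabulates washout and placebo AEs, and the July 2017 protocol randomizes 1:1 to placebo in Period 4. What is particular to run-in is that it precedes all exposure.

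A reader might also infer that background events would be reported as drug-related. SAP 7.8.1 defines drug-related by causality (possible, probable or definite) and tabulates those events separately. Background events raise TEAE counts, but they do not become drug-related by default.

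Finally, medication withdrawal may itself raise run-in rates, so run-in could overstate the background during dosing. That is correct, and it is why the summary should be descriptive.

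**Conclusion.** The contradiction is real, and the SAP drops a promised summary without disclosing it. At stake is the one drug-naive AE reference, 560 planned patient-days in Stage 2, gathered under the run-in medication restrictions (with the proton pump inhibitor difference noted above). Also at stake is the pre-dose severity used to judge worsening. The 560 assumes that all 40 patients complete run-in. How much is actually missing depends on which section sites followed and on the fields of the Medical History CRF, and the documents show neither. They therefore support saying that the reference is at risk, not that it is lost. The point is minor: it leaves the sample size and the primary efficacy test unchanged, but it bears on how a primary safety objective is read.

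**What to change.** In the protocol, set consent as the single start of AE collection in 9.10, 9.12, 9.13 and 9.14, and replace the medical-history rule in 9.14 with recording on the AE form.

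In the SAP, add a run-in (pre-treatment) AE summary by system organ class, preferred term and grade, with patient-days because the periods differ in length. State that it is descriptive and that medication withdrawal may raise run-in rates. Section 9.10 promises a separate summary but not this layout; the patient-days are a recommendation. If the sponsor prefers to keep only the listing, SAP 5.1 and section 9 should say that the summary was dropped.

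For patients already past run-in, check whether medical-history entries arising after consent can be identified, and report how many there are.

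The cost is protocol and SAP wording and one table. The run-in contacts already include AE review, so no visit or procedure is added.
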